2.4 We will use resting state functional connectivity MRI (fMRI) to directly test the hypothesis that tDCS strengthens fronto-limbic connections involved in emotional processing. Resting state functional connectivity MRI (fMRI) is a recently evolving method from which functional connectivity between distant brain regions is extracted based on low-frequency fluctuations. It allows for the identification of discrete functional networks in the brain. Distributed networks of brains regions have been shown to display temporally correlated patterns of spontaneous activation. This temporal coherence tends to occur in the brain regions that are anatomically connected (Zhang and Raichle 2010). Furthermore, functionally connected networks derived using resting state approaches mirror activation patterns found in task-based functional imaging studies. For clinical purposes, the strength and nature of network connections can be compared in clinical and healthy populations, or resting state can be used in a repeated measures fashion to assess changes within clinical groups. Resting state fMRI had been employed in a small number of studies of TBI patients to examine how network connectivity changes with recovery (Nakamura, Hillary et al. 2009; Hillary, Slocomb et al. 2011).

3. Study Design.

Forty (40) individuals status post TBI with complaints of emotional dysfunction 6 months post-brain injury and twenty-five (25) healthy controls will participate in the study. We expect a

total of 65 subjects to enroll. After obtaining informed consent, they will be screened to ensure that they meet inclusion-exclusion criteria at Visit 1. At visit 1 subjects also will be tested on chemosensory performance evaluation using Sniffin' sticks test and oculomotor movement evaluation using King-Devick test Subjects meeting criteria will then be tested at baseline on neuropsychological assessments, tests of attention (at Visit 2), and the emotional function battery (at Visit 3). The TBI subjects will also undergo resting-state MRI (at Visit 4).

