1. Number of Subjects. Forty (40) patients with complaints of emotional dysfunction 6 months post-brain injury between 18 and 85 years of age, and twenty-five (25) healthy control subjects will participate. The patients will be referred after discharge from the inpatient brain injury units of Bellevue Hospital and Hospital for Joint Diseases and from their outpatient TBI clinics, and will meet the inclusion-exclusion criteria listed below.

- 2. Gender of Subjects.** Both male and female subjects will be included. We will attempt to recruit 50% of male and 50% female subjects. There will be no gender based enrollment restrictions.
- 3. Age of Subjects.** The age range of subjects is between 18 and 85 years. The goal of this study is to understand emotional dysfunction in adult patients. Individuals below the age of 18 will be excluded from this study since pediatric TBI is relatively rare and the mechanisms of recovery may differ. Adults over 85 will be excluded to rule out possible confound of co-morbid medical conditions.
- 4. Racial and Ethnic Origin.** There are no exclusions based on gender or ethnic group.
- 5. Inclusion Criteria.**
 - (1) Brain Injury at least 6 months prior.
 - (2) Family or self-identification of cognitive or emotional difficulties.
 - (3) Unchanged and stabilized medical treatment in the three weeks prior to the screening.
- 6. Exclusion Criteria.**
 - (1) Any social or medical problem that precludes completion of the protocol.
 - (2) Presence of focal motor deficits in the upper extremities.
 - (3) Comorbid psychiatric disease such as schizophrenia, or active substance abusers (except nicotine).
 - (4) History of craniectomy, active infection, or seizure activity beyond 1 week post-TBI.
 - (5) Complicating medical problems such as uncontrolled hypertension, diabetes with signs of neuropathy, and previous neurological illness such as head trauma, prior stroke, epilepsy or demyelinating disease, implanted neuromodulatory or electronic device, metal in head
 - (6) Pregnancy

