- 7. Vulnerable Subjects.** Although TBI patients have some cognitive impairment, we will only consent patients who have been determined to have the capacity to give consent. This determination will be made by [name], [name] Im or [name] who are specialists in Brain Injury and will screen patients to determine if they are in a stable cognitive state, whose capacity to give consent is not expected to fluctuate. Only such patients will be enrolled in the study. We will provide information to the subjects in terms that they can fully understand, and capacity to consent will be determined by the subject's verbal understanding of the protocol as determined by the PI. We will not exert any overt or covert coercion, and no financial incentive will be offered. The consent document that each potential subject will be asked to sign will be written in the language that he or she understands, and will be approved by the IRB.

III. METHODS AND PROCEDURES

1. Methods and Procedures.

Patients will sign informed consent and be required to undergo self-assessment (using the TIRR symptom checklist), caregiver assessment (using the Neurobehavioral Functioning Inventory/NFI), and clinician assessment (using NRS-R) to determine neurobehavioral status on study entry. Screening procedures will also include medical history and interview, review of medications and imaging records to ensure that participants meet inclusion/exclusion criteria. Screening procedures will take place at the Motor Recovery Laboratory. The following outcome measures will be administered at baseline and at the end of the 6-week tDCS intervention.

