1.5 Intervention with active and sham tDCS and computerized cognitive re-training

After providing informed consent approved by the IRB of New York University School of Medicine (NYUSoM), all patients will undergo testing with the above listed outcome measures. They will then be randomized into the two intervention groups, the groups being (1) tDCS + cognitive re-training, and (2) sham tDCS + cognitive re-training. The intervention will be carried out for 20 minutes twice a week for 6 weeks during which the subjects in each group will be engaged in re-training using visual cognitive re-training software programs for 30-45 minutes during each session (www.positscience.com). These re-training programs have been used in patients with TBI and have been shown to be effective (Fisk, Novack et al. 2002; Calvanio, Williams et al. 2004; Novack, Banos et al. 2006). Cognitive re-training will thus be individualized to each patient's cognitive level, but still be systematic, and will not need direct one-on-one supervision by a neuropsychologist.

Transcranial direct current stimulation will be delivered by trained study personnel using the saline-soaked pair of surface sponge electrodes (35 cm²) delivered by a specially developed, battery-driven, constant direct current stimulator (Fisher Wallace Cranial Stimulator, Fisher Wallace Laboratories, New York) with a maximum output of 4 mA (**Fig. 1**). FDA approval: The Cranial Stimulator is an FDA cleared device indicated for application of electrical stimulation to a patient's head to treat insomnia, depression, or anxiety. TBI subjects experience insomnia, depression and anxiety and all subjects enrolled in this study will have some combination of these problems. The purpose of this study is to understand the mechanisms behind the depression, anxiety and insomnia that patients with TBI experience. The hypothesis is that emotional dysregulation contributes to the symptoms. This device will therefore be used in alignment with FDA clearance indications. To stimulate the DLPFC, the anode electrode will be placed over F3 according to the 10-20 international system for EEG electrode placement (Fregni, Boggio et al. 2005) (**Fig.2**). The cathode will be placed over the contralateral supraorbital area.

Fig.1. FDA approved Fisher Wallace Cranial Stimulator.

[figure not shown]

Fig.2. Placement of electrodes (Rosa and Lisanby 2012).

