We will focus our investigations on the left DLPFC, as modulation of this area by tDCS has been shown to enhance working memory (Fregni, Boggio et al. 2005) which also demands similar attentional resources as emotional control (Anderson and Knight 2010). A constant current of 2 mA intensity will be applied for 20 min. Patients will feel the current as an itching sensation at both electrodes at the beginning of the stimulation. For sham stimulation, the electrodes will be placed in the same position; however, the stimulator will be turned off after 5 seconds (Siebner, Lang et al. 2004) so that patients will feel the initial itching sensation in the beginning, but receive no current for the rest of the stimulation period; this procedure has

been used to blind patients to the stimulation condition (Nitsche, Liebetanz et al. 2003; Nitsche, Schauenburg et al. 2003).

2. Data Analysis and Data Monitoring.

Power Analysis: This is a pilot feasibility study hence sample size is small and arbitrary. Power analysis from these pilot data will be used to determine sample size in future studies. Subjects with TBI will be randomized to the 2 treatment groups n=10 in each group.

Data Analysis:

1) To examine the relationship between alerting, orienting and executive attention and emotional recognition, reactivity and regulation in patients with TBI and controls.

Hypothesis: Patients with TBI will show clear patterns of attentional and emotional impairment compared with controls. Deficits in executive attention will be related to deficits in emotional appraisal in patients.

Scoring of emotional recognition, reactivity and regulation:

- 1) **Emotional reactivity film clips:** Physiological responses (cardiac inter-beat, finger pulse amplitude, finger pulse transmission time, ear pulse transmission time, and respiration period) will be recorded, and input from baseline will be subtracted from input across the most intense segment of the clip. Data will be combined into a single aggregate score for each diagnostic group to increase reliability and reduce noise; aggregate scores of patients and controls will then be compared. Facial behavior will be recorded and coded for displays of the target emotion across the most intense segment of the clip; data from patients and controls will then be compared.

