- 2) **Emotional recognition:** Responses to emotion recognition questions, using both the reactivity film clips described above and picture stimuli will be recorded and coded; coded data from patients and controls will be compared.
- 3) **Emotional regulation with disgust videos:** For the three conditions, physiological responses (as described above) will be recorded, and input from baseline will be subtracted from input across the most intense segment of the clip. Facial behavior will be recorded and coded. Data from patients and controls will be compared.

For coding facial behavior, coders will be blind to the diagnostic status of the participant and code videos with sound muted; coding will be assessed for inter-rater reliability

Pearson's correlation analysis will be performed to examine the relationship between reaction time (RT) scores indicating alerting, orienting and executive attention on the ANT-R and emotional recognition, reactivity and regulation scores. Differences in patients and controls will be computed. We will also correlate the clinical scores on the MARS with the ANT-R and the TAS-20 scores with the emotional battery scores. We expect that deficits in selective or executive attention will be related to deficits in emotional appraisal in the patients.

2) To determine whether anodal tDCS applied over the dorsolateral prefrontal cortex in conjunction with computer assisted cognitive re-training of attention will lead to greater improvement in attention and/or emotional regulation compared with sham-tDCS + cognitive re-training. Hypothesis: Patients receiving tDCS + cognitive re-training will show greater improvement in post-intervention measures of attention and emotional regulation.

A 2 (condition) x 2 (pre and post session) repeated measures ANOVA with a priori orthogonal contrasts will be performed on the variables related to executive attention and emotional appraisal to determine whether there is a difference both within and between groups. This analysis will also provide data for power analysis to determine the sample size for subsequent interventional studies. We expect that patients receiving tDCS + cognitive re-training will show greater improvement in post-intervention measures of attention and emotional regulation.

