
To stimulate the DLPFC, the anode electrode will be placed over F3 according to the 10-20 international system for EEG electrode placement (Fregni, Boggio et al. 2005). The cathode will be placed over the contralateral supraorbital area. We will focus our investigations on the left DLPFC, as modulation of this area by tDCS has been shown to

enhance working memory (Fregni, Boggio et al. 2005) which also demands similar attentional resources as emotional control (Anderson and Knight 2010). A constant current of 2 mA intensity will be applied for 20 min. These stimulation parameters have been used in other tDCS studies (Fregni, Boggio et al. 2006; Fregni, Boggio et al. 2006; Stevanovic 2011), and have been shown to produce effects outlasting the stimulation, well within safety limits [see detailed review in (Stevanovic 2011)]. To date, the above described stimulation parameters have not elicited any treatment-related serious adverse events. Non-serious adverse events infrequently occurring in tDCS studies (Poreisz, Boros et al. 2007) include short-term headache, transient fatigue or disturbed sensation under electrodes during the stimulation, such as mild tingling, itching or mild burning that is a natural sensation related to low-intensity current passing through the scalp. The sensation typically disappears immediately after the tDCS stimulation. Further, tDCS has not presented with any potentially harmful pharmacological interactions (Nitsche and Paulus 2001; Poreisz, Boros et al. 2007). Thus study participants receiving tDCS maintain their usual pharmacological regimen.

Patients having brain scans as part of the research study may feel claustrophobic from lying in the magnetic tube. There is risk of injury if there are metal objects in the body. Subjects will be required to fill out a questionnaire indicating if this is true. The subjects will be told that they may hear loud noises while in the MRI machine. The distress will be minimized by providing the subjects with ear plugs and limiting the duration of time in the MRI machine to less than 30 minutes. The research MRI scans will be read by the investigators within one week of the exam. If a previously undetected, clinically significant finding is observed the subject will be notified by the PI by phone so that the matter may be investigated further with the subject's regular physician.

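### Aim 1 compares patients who may be on stable drug treatment with healthy controls who have no drug criterion or matching, so a drug that blunts cardiac, pulse or respiratory responses can be read as a TBI deficit

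*Protocol*

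**What the plan says.** Aim 1 hypothesises that patients with TBI are impaired in attention and emotion relative to controls. The places that matter are these.

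- **Patients' treatment at entry** (Protocol II.5, Inclusion Criteria): "Unchanged and stabilized medical treatment in the three weeks prior to the screening". No washout is stated and no drug class is excluded. II.6 excludes hypertension only when uncontrolled.
- **Patients' symptoms** (III.1.5, Intervention): after naming insomnia, depression and anxiety in TBI, the text says that "all subjects enrolled in this study will have some combination of these problems".
- **Controls** (I.3, Study Design): "twenty-five (25) healthy controls will participate in the study". The protocol states no matching, no rule on their medication and no criteria specific to them.
- **Medication data** (III.1, Methods and Procedures): "Screening procedures will also include medical history and interview, review of medications and imaging records". The stated purpose of this review is to confirm eligibility.
- **Outcome** (III.2, Data Analysis, reactivity film clips): "Physiological responses (cardiac inter-beat, finger pulse amplitude, finger pulse transmission time, ear pulse transmission time, and respiration period) will be recorded". The baseline value is subtracted from the most intense part of the clip, the measures are pooled into one score per diagnostic group, and the two groups' scores are compared. The disgust films use the same measures.
- **Comparison** (III.2, recognition and disgust films): the text says only that "data from patients and controls will be compared". No covariate, stratum or sensitivity analysis for medication is named.

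**The concern.** The outcomes are heart period, pulse amplitude, pulse transit times and breathing period. Drugs acting on the heart, the circulation or alertness can alter these directly, whatever the person feels. The protocol leaves room for such drugs in the patients. Treated hypertension is eligible, mood and sleep symptoms are expected throughout, and the section on potential benefits (IV) presents tDCS as an add-on for patients with partial relief from drugs. In a group called healthy, such drugs should be less common.

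Diagnosis and drug exposure are therefore likely to go together. A smaller autonomic response in patients could then be reported as reduced emotional reactivity or altered regulation after TBI when part of it is pharmacological. The study is meant to supply pilot data for further funding, so a confounded contrast would carry into the next design.

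**Working it through.** The protocol gives no error rate, effect size or SD for Aim 1 and calls its sample size arbitrary. There is no planned figure to reproduce, and what follows is illustrative.

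**Inputs from the protocol**
- Patients: 40 (II.1: "Forty (40) patients with complaints of emotional dysfunction 6 months post-brain injury"). I.3 and III.2 also give two randomised groups of 10, which implies 20, so both are shown.
- Controls: 25.

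**Assumptions**
- Two-sided 5% test, SD of the change score 1, no true TBI effect.
- A fraction *p* of patients takes a drug that damps the score by *d* SD. No control does, unless stated.

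**Step 1: what baseline subtraction removes.** With an additive drug effect on resting level only (0.8 SD in half of the patients), the effect cancels in the change score. In 20,000 simulated trials with 40 v 25 the rejection rate was 4.8%. With damping of the response by 0.5 SD in half of the patients, the rate was 15.8% (40 v 25) and 12.9% (20 v 25).

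**Step 2: bias and false-positive rate.**

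Bias = *pd*.

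Standard error = √[(1 + *p*(1−*p*)*d*²)/n₁ + 1/25], where n₁ is the number of patients.

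Noncentrality = bias / standard error, with the rejection probability taken from the noncentral t on n₁ + 23 degrees of freedom.

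Example, *p* = 0.5, *d* = 0.5, n₁ = 40: bias 0.25; SE = √(1.0625/40 + 0.04) = 0.258; noncentrality 0.97; rejection rate 15.9%.

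| Share of patients on drug | Blunting (SD) | Bias (SD) | 40 v 25 | 20 v 25 |
|---|---|---|---|---|
| 25% | 0.5 | 0.125 | 7.7% | 6.9% |
| 50% | 0.5 | 0.25 | 15.9% | 12.6% |
| 75% | 0.5 | 0.375 | 30.0% | 22.6% |
| 50% | 0.8 | 0.40 | 32.3% | 23.9% |

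These are selected cases, not bounds. The extreme corner (75% on a drug, 0.8 SD) gives 62% and 47%. In the other direction, if 10% of controls also take such a drug, the 50%/0.5 SD case falls to 11.8% with 40 v 25.

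**Step 3: dilution in the aggregate.** Suppose the five measures are independent, are averaged, and the drug moves only one of them by 0.5 SD. The aggregate then moves by 0.5/√5 = 0.22 of its own SD. With half of the patients treated, the bias is 0.11 SD and the false-positive rate about 7% (40 v 25).

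**Step 4: the attention–emotion correlation within patients.** If a drug taken by a fraction *p* shifts both scores by *d*, the induced correlation is *r* = *p*(1−*p*)*d*² / [1 + *p*(1−*p*)*d*²]. With *p* = 0.5, *d* = 0.5 gives *r* = 0.059 and a rejection rate of 6.5% at n = 40; *d* = 0.8 gives *r* = 0.138 and 13.5%. These rates assume that the drug shifts the ANT-R network score itself.

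**The case against.** **Adjustment may be in the SAP.** The protocol says only that data are compared, which does not rule out covariates. That stands: a reader might infer that the comparison will certainly be unadjusted, but the text shows only that no adjustment is named. Two features do belong to the protocol: the absence of any drug rule or matching for controls, and a score formed per diagnostic group. Read literally, that score leaves no personal value to adjust.

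**The drug difference is inferred.** A reader might conclude that the groups differ in medication and that the result will be biased. The documents give drug use for neither group. The inclusion criterion permits stable treatment without saying that anyone takes drugs, and III.1.5 lists symptoms, not prescriptions. The supportable wording is that a drug effect can be read as a deficit.

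**The statement on keeping usual drugs is about another period.** Section IV says "Thus study participants receiving tDCS maintain their usual pharmacological regimen". It concerns participants receiving stimulation, whereas the patient–control tests come before stimulation starts. Only the entry criterion bears on drug use at baseline.

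**Sedation and ANT-R.** A reader might infer that slower reaction times would create the hypothesised correlation. The ANT-R section of III.1.1 measures alerting and orienting by changes in reaction time and executive attention by a flanker contrast, so general slowing largely cancels. Even without that cancellation the effect is small unless the drug effect is strong.

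**Scope.** Recognition answers and blinded facial coding are separate channels from the autonomic measures. Randomisation protects the active–sham comparisons of Aims 2 and 3 from this confounding. Both limits stand.

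**Conclusion.** The point holds for the physiological part of Aim 1. Patients may be tested on stable medication, controls have no drug criterion or matching, and the outcomes are ones that drugs can act on directly. Baseline subtraction does not remove blunting of the response, so an observed difference cannot be assigned to TBI alone.

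The size cannot be taken from the documents. In the four tabulated cases the false-positive rate is about 8% to 32% with 40 v 25 and about 7% to 24% with 20 v 25. It is nearer 7% if only one of five independent components is affected by 0.5 SD in half of the patients. All of this rests on assumed shares and drug effects and, except where shown, no medicated controls.

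The claim about the correlation is secondary. Because the fix is cheap, the change should be made even in a pilot.

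**What to change.** 1. From the Visit 1 medication review, code for every patient and every control whether a drug acting on heart rate, circulation or alertness is in use at baseline testing.
2. Compute the physiological score for each person, not one per diagnostic group.
3. Beside the unadjusted patient–control difference, report a sensitivity analysis restricted to subjects without such drugs. Add a covariate-adjusted estimate only if enough controls are medicated to support it. With no medicated controls, the group coefficient adjusted for the drug indicator is simply unmedicated patients minus controls, which repeats the restricted estimate.
4. State in advance that, if the physiological difference shrinks materially in that analysis, the report will say that it is not attributable to TBI alone, and will note that unmedicated patients may be less severely injured.
5. If the correlation is examined for drug effects, limit this to an exploratory partial correlation given the drug indicator.

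The cost is a few sentences and one coded variable from a review already planned, with no added visits. The downside is a smaller and possibly milder subgroup. If half of 40 patients were excluded, the standard error would rise from √(1/40 + 1/25) = 0.255 SD to √(1/20 + 1/25) = 0.300 SD. If half of 20 were excluded, it would rise from 0.300 to √(1/10 + 1/25) = 0.374 SD. For that reason the analysis sits beside the main result and does not replace it. No change to any patient's medication is implied.

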1.1 NeuroCognitive Testing

Neurocognitive Domains	Neurocognitive Measures
Premorbid Functioning	Wechsler Test of Adult Reading (Wechsler 2001) n = 60, a = .95 Time = 10 min
Attention/Working Memory	Trails A (Reitan and Wolfson 1985) n = 25, a = .73 Time = 3 min WAIS Subtest: Digit Span (Wechsler 2008) n ~ 16, a = .94 Time = 4 min Auditory Consonant Trigrams (Peterson and Peterson 1959) n = 20, a = .85 Time = 10 min
Executive Function	Trails B (Reitan and Wolfson 1985) n = 25, a = .87 Time = 5 min Stroop Color-Word (Golden 1978) n ~ 300, a = .83-.91 Time = 5 min
Information Processing Speed	Symbol Digit Modalities Test (Smith 1993) n ~ 110, a = .80 Time = 5 min

n = # items; a = alpha; Time = time to administer

Premorbid Neurocognitive Functioning:

Wechsler Test of Adult Reading (Wechsler 2001). The WTAR estimates pre-morbid intellectual functioning for adults (16-89 years old). Thus, it allows for the identification of relative impairments by detecting discrepancies between levels of premorbid functioning and current functioning. This is particularly important for detecting impairment in higher functioning individuals, who may currently have average performance where they performed in the superior range premorbidly.

Attention/Working Memory:

Trails A (Reitan and Wolfson 1985) is a test of attention and complex visual scanning with a psychomotor speed component. Trails A requires individuals to connect randomly arranged numbers sequentially from lowest to highest number. Like many attention and motor speed measures, Trails A is sensitive to cognitive decline.

Digit Span (Tulsky, Zhu et al. 1997) requires the respondent to recall digits forward and backward and is used to measure working memory. Although forward span usually remains stable and resistant to brain disorders (Lezak, Howieson et al. 2004), individuals with diffuse

damage (e.g., mild TBI) can have mental tracking difficulties and those with more severe TBI can perseverate from previous items (Ruff, Evans et al. 1986). However, backward span is more sensitive to brain disorders, particularly diffuse damage which is characteristic of TBI (Fork, Bartels et al. 2005).

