Auditory Consonant Trigrams (Peterson and Peterson 1959) is a test of information processing and divided attention. Three consonants are presented to the individual, who must remember them after intervals of 0, 9, 18 and 36 seconds. During intervals, the person is required to count backwards aloud by threes from different starting points. The task captures everyday experience of momentary distraction and subsequent loss of recently learned information and can identify dysfunction following mild neurological changes (Boone 1999).

Executive Function:

Stroop Color-Word Test (Golden 1978) is a measure of selective attention, verbal processing speed, cognitive flexibility and response inhibition. Poor performance on the Stroop has been found to be associated with frontal systems dysfunction secondary to closed head injury (Trenerry, Crosson et al. 1989). The test is a good discriminator between individuals with TBI and controls (Asikainen, Nybo et al. 1999; Bate, Mathias et al. 2001; Wallesch, Curio et al. 2001).

Trails B (Reitan and Wolfson 1985) is a speeded test of attention, sequencing, mental flexibility, visual search and psychomotor speed. The participant draws lines connecting alternating circles with numbers and letters in sequence. Speed of performance on Trails B is considered to be vulnerable to the subtle cognitive effects of TBI (Lezak 1995; Rasmusson, Carson et al. 1996). Test-retest reliability over two weeks was reported as .44 in a non-disabled sample and .67 in people with disabilities. Trails B errors are considered valid measures of dorsolateral prefrontal dysfunction (Stuss and Levine 2002).

Information Processing Speed:

Symbol Digit Modalities Test (Smith 1993) is used to measure visual scanning, tracking and motor speed, and it is sensitive to subtle cognitive impairment. A score below 1.5 standard deviations below the mean is indicative of cerebral dysfunction. Performance declines are observed with increasing age, demonstrating that cognitive changes could be detected with this measure. This test is sensitive to brain injury (Lezak 1995; Spreen and Strauss 1998).

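### Aim 1 compares patients with controls and correlates attention with emotion scores without age adjustment, although ages run from 18 to 85 and no matching of controls is stated

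*Protocol*

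**What the plan says.** Aim 1 concerns how three attention networks (alerting, orienting, executive) relate to emotional recognition, reactivity and regulation in patients with TBI and in controls.

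- **Correlation (III.2, Data Analysis, Aim 1).** "Pearson's correlation analysis will be performed to examine the relationship between reaction time (RT) scores" from the ANT-R and the emotion scores. The next sentence is "Differences in patients and controls will be computed". Neither sentence names a covariate or says whether the correlation is pooled or within group.
- **Group contrast (same section).** Physiological, facial and recognition data from patients and controls are to be compared. No adjustment is named.
- **Age (II.3).** "The age range of subjects is between 18 and 85 years".
- **Samples (II.1).** The patient sample is set at 40. For the comparison group, "twenty-five (25) healthy control subjects will participate". No matching and no control-specific criteria are given. Inclusion criteria 1 and 2 (prior brain injury, cognitive or emotional difficulties) can apply only to patients.
- **Where the link is expected.** The Aim 1 hypothesis and the sentence that closes the Aim 1 analysis text both place the link between executive attention and emotional appraisal in patients.
- **Premorbid ability (III.1.1).** "The WTAR estimates pre-morbid intellectual functioning for adults". It is collected at baseline but appears in no Aim 1 analysis.

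**The concern.** The patient-control contrast is not randomised, so nothing in the design balances age. Patients come from named brain injury units and clinics; no source is given for controls. If the two groups differ in age and the scores vary with age, the unadjusted difference mixes the effect of TBI with the effect of age.

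The correlation has a related problem that does not depend on the controls. Over a range as wide as 18 to 85, age may be a common cause of a poorer attention score and a poorer emotion score. A bivariate Pearson coefficient then differs from zero even if, at any given age, the two are unrelated.

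The results are meant to support an application for external funding. A deficit or an attention-emotion link that age could explain would be a weak basis for the next study.

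**Working it through.** The protocol states no alpha, power, effect size or correlation for Aim 1, so there is no planned figure to reproduce. The check asks how far age alone could move a nominal two-sided 5% test.

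**Inputs from the protocol:** 40 patients and 25 controls (II.1); ages 18 to 85 (II.3). The patient number is itself unclear, because III.2 says "Subjects with TBI will be randomized to the 2 treatment groups n=10 in each group", which makes 20. Both are shown.

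**Assumed inputs:** correlation ρ between age and each score, 0.3 to 0.5; a difference in mean age of 0.5 SD. If ages were uniform over 18 to 85, the SD would be 67/√12 = 19.3 years, so 0.5 SD would be about 10 years. That distribution is also an assumption.

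**1. Correlation within patients, no link at a given age.** The induced correlation is r = ρ × ρ. Rejection rates come from 20,000 simulated data sets per case.

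| ρ | induced r | n = 40 | n = 20 |
|---|---|---|---|
| 0.3 | 0.09 | 8.4% | 6.5% |
| 0.4 | 0.16 | 16% | 11% |
| 0.5 | 0.25 | 35% | 18% |

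Closed-form check at ρ = 0.5, n = 40, by Fisher z: atanh(0.25) × √37 = 0.2554 × 6.083 = 1.55. The probability of exceeding 1.96 is then Φ(1.55 − 1.96) = Φ(−0.41), about 34%, in agreement.

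**2. Same correlation, adjusted for age (partial correlation, n = 40).** Rejection returns to between 4.6% and 5.2% for ρ from 0 to 0.6.

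**3. Patient-control contrast, no true group effect.** Bias in SD units = ρ × age gap in SD.

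- Gap 0.5 SD: bias 0.15 (ρ = 0.3) to 0.25 (ρ = 0.5); simulated rejection 8.9% to 16%.
- Check: the SE of a standardised difference is √(1/40 + 1/25) = 0.255. Then 0.25/0.255 = 0.98, and Φ(0.98 − 1.96) is about 16%.
- A larger gap of 1 SD gives 21% to 49%.

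**4. Pooling, if it were done.** With 40 and 25 subjects, zero correlation within each group and a separation of d SD on both scores, r = pq·d²/(1 + pq·d²), where pq = (40/65)(25/65) = 0.237. At d = 0.8, r = 0.13 and rejection is 18%; at d = 1.0, r = 0.237/1.237 = 0.19 and rejection is 34%. Computed within patients only, at d = 1.0, rejection is 5.3%.

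**The case against.** Several points on the other side have force.

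- **Pooling.** A reader might infer that group separation alone could produce the hypothesised relationship. The protocol does not support that: it places the relationship in patients, where a difference between groups cannot create a correlation. The figures in step 4 apply only if the correlation sentence, which names no group, is read as covering all 65 subjects. This objection stands.
- **Matching.** A reader might say that the controls are unmatched. The protocol is silent; it does not say so. What can be said is that no matching is stated.
- **Evidence for an age effect.** The sentence "Performance declines are observed with increasing age" is about the Symbol Digit Modalities Test, which is not in the Aim 1 correlation. The ANT-R scores are changes in reaction time between conditions, which remove part of general slowing, and the physiological scores are baseline-subtracted. Nothing in the protocol says that the emotion scores worsen with age. The age correlations are therefore assumptions, and at 0.3 the inflation is small.
- **A later analysis plan.** A covariate list could sit in a statistical analysis plan that is not shown, and naming Pearson does not strictly exclude a partial correlation. This stands in part. The protocol does name a method, and for the imaging model in Aim 3 it states covariates, so a reader would take Aim 1 as unadjusted. How controls are chosen is a matter of design and belongs in the protocol.
- **Pilot status.** The sample size is described as arbitrary. That limits the precision expected of Aim 1; it does not remove a bias that is cheap to avoid.

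**Conclusion.** The point holds in a limited form. As written, Aim 1 relies on unadjusted comparisons and bivariate correlations in a non-randomised contrast over a wide age range. Both the group difference and the within-patient correlation can therefore be partly age artefacts.

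The size depends on how strongly age relates to the scores and on any age gap between groups, neither of which the protocol gives. Over the assumed range, inflation of the within-patient test runs from slight to serious; it is lower if only 20 patients contribute. For the group contrast it is moderate at a half-SD gap and disappears if the groups happen to be alike in age. The missing group in the correlation sentence is a point of wording to settle, not evidence that pooling is planned.

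**What to change.** Amend the Aim 1 analysis text to say:

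1. Patients and controls are compared with a model that includes age. The premorbid reading score (WTAR) may be added as a sensitivity covariate.
2. Attention-emotion correlations are partial correlations adjusted for age, computed separately in patients (primary) and in controls.
3. Any estimate that pools the two groups includes a group term.

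In II.1, state how controls are recruited and whether they are matched on age, and give one number for the patients who enter Aim 1.

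The cost is one or two degrees of freedom and a change of wording. Age has to be known for eligibility, and the WTAR is already in the baseline battery, so no new data are needed.

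The calculation assumed a linear age effect. With ages up to 85 it would be sensible to check that assumption when the model is fitted.
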